13.10.5 Primary Efficacy Endpoint

The primary endpoint in the study will be the time to relapse measured from the day that Ketamine infusion was started.

Relapse is a time to event outcome reflective of this multi-component disorder. Time to relapse is more sensitive measure than an assessment at a fixed time. Time to relapse will be displayed using a Kaplan-Meier lifetable with the treatment groups compared using a two-sided Wilcoxon-Gehan test and a proportional hazard model to include the above cited covariates.

Relapse will be judged in real-time by the study physician using baseline measures of depression and suicidality as a guide.

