5. OBJECTIVES

5.1 Primary Objective

The primary objective of the study is to test the hypothesis that following response to initial ketamine infusion, experimental drug NRX-101 (DCS + lurasidone) is superior to lurasidone alone and placebo as oral-therapy for delaying time to relapse (resulting in a new treatment plan or the subject relapsing to baseline levels of depression or suicidality) in subjects with documented bipolar depression presenting with symptoms of depression and suicidal ideation.

The primary study hypothesis (alternative hypothesis) is that ketamine and experimental drug NRX-101 (K/N) delays the time to documented relapse as compared to both lurasidone (L) and placebo (P) as measured by the hazard ratio (h) versus the null hypothesis of no delay in time to relapse for either comparator treatment (ketamine/lurasidone [K/L] and ketamine/placebo [K/P]) as follows:

$$H_0: h_{\text{NRX-101}} < h_L \text{ and } h_P$$

$$H_a: h_{\text{NRX-101}} \geq h_L \text{ and } h_P.$$

The primary outcome measure will be time to relapse, defined as the need to implement a new treatment plan or a return to baseline levels on the Columbia-Suicide Severity Rating Scale (C-SSRS), or the Montgomery Asberg Depression Rating Scale (MADRS) subset on the Bipolar Inventory of Symptom Severity (BISS).

All relapses will be documented by the site physician and reviewed on a monthly basis by a Relapse Adjudication Committee. The Relapse Adjudication Committee (RAC) will determine whether the relapse met the primary endpoint criteria.

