Subjects who meet study criteria for relapse at any point during the study will be withdrawn from the study and offered clinically-appropriate treatment as determined by the treating study physician, which may

include inpatient hospitalization, repeated administration of ketamine, electroconvulsive therapy (ECT), or other treatments determined by professional judgment. Subjects who demonstrate therapeutic benefit from experimental drug NRX-101 (DCS+ lurasidone) at study completion may be offered prescribed DCS by their treating psychiatrist.

The Schedule of Study Activities (Table 3) summarizes the frequency and timing of efficacy, PK, and safety measurements applicable to this study. With the exception of post-dose assessments, visit-specific subject-reported outcomes assessments should be conducted or completed before any tests, procedures, or other consultations for that clinic visit to prevent influencing subject perceptions. A recommended order of study procedures will be provided to sites as a separate document.

Actual dates and times of assessments will be recorded in the source documentation and electronic Case Report Form (eCRF).

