8.2.5 Outcome and Safety Measures

8.2.5.1 Outcome Measures

8.2.5.1.1 Primary Efficacy Endpoint

The primary outcome measure will be time to relapse, defined as (1) a return to a score of ≥ 4 on the C-SSRS, (2) a score of ≥ 20 on the MADRS subset of the BISS following a response to

ketamine at 24 hours, or (3) the treating physician's determination that a change in treatment plan, such as re-hospitalization, ECT, or addition of new antidepressant drugs is required.

All site-defined relapses will be adjudicated by a Relapse Adjudication Committee (RAC) which will review documentation provided by the site for each incidence and determine whether the relapse meets the protocol definition of relapse. The RAC will meet monthly. The RAC is authorized to determine that relapse occurred even if the site does not make this determination.

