Examples (not all-inclusive)	
 • Failure to obtain informed consent • Informed consent obtained by an unauthorized individual • Enrollment of a subject who did not meet eligibility criteria for whom a protocol exception was not obtained • Performing a study procedure that is not approved by the IRB and/or is not in the protocol • Failure to perform a required lab test that, in the opinion of the Site Investigator, may affect subject safety or data integrity • Failure to perform or follow a study procedure that, in the opinion of the Site Investigator, may affect subject safety or data integrity • Failure to follow safety (AE) management plan • Failure to report a SAE to the IRB and/or Coordination Center 	
 • Implementation of unapproved recruitment procedures • Only a photocopy of the signed/ dated consent form is available (the original is missing) • Pages are missing from the signed/ dated informed consent form • Use of invalid consent form (i.e., without IRB approval or outdated/expired form) • Failure to perform or follow an approved study procedure that, in the opinion of the Site Investigator, does not affect subject safety or data integrity • Study procedure conducted out of sequence • Failure to perform a required lab test • Missing lab results • Study Visit out of approved window • Over-enrollment • Enrollment of subjects after IRB approval of the study has expired • Failure to submit a continuing review application to the IRB before study expiration
Reporting Requirements	
 • Record the date discovered, date occurred, description of event in the Protocol Deviation Log. • Notify the Coordinating Center within 24 business hours. 	
 • Record the date discovered, date occurred, description of event in the Protocol Deviation Log. • Notify the Coordinating Center

A Relapse Adjudication Committee (RAC) will be assembled and managed by MGH CTNI. All site-reported relapse events will be reviewed by the RAC, and a determination made as to whether the event met study criteria for relapse. The results of each adjudication will be entered into the study database. The RAC will meet monthly to adjudicate the events.

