11. ASSESSMENT OF EFFICACY

The primary outcome measure will be time to relapse, defined as a return to a score of ≥ 4 on the C-SSRS, and/or a score of 20 on the MADRS subset of the BISS. The RAC will adjudicate each site reported instance of relapse for compliance the protocol definition of time to relapse.

Relapse is a time-to-event outcome reflective of this multi-component disorder. Time to relapse is more sensitive measure than an assessment at a fixed time. Time to relapse will be displayed using a Kaplan-Meier lifetable with the treatment groups compared using a two-sided Wilcoxon-Gehan test and a proportional hazard model to include the above cited covariates.

Titration of DCS or lurasidone within the dosing range will not be considered to be a relapse.

All of the instruments used to measure ASIB or depression constitute serial continuous and ordinal outcomes which will be analyzed using MMRM, which accounts for missing data and early discontinuations. These instruments include the following:

- C-SSRS (and the retrospective C-CASA component)
- CHRT (CHRT-SR and CHRT-C)
- BISS
- SIBQ
- BPRS

The models will include treatment group, study visit, the interaction between study visit and treatment group, the baseline of the variable being analyzed, C-SSRS 24 hours post infusion (1, 2), age (<25 yrs, 25-39 yrs, >40 yrs), and gender as fixed effects. The reason for missing data will be evaluated as a condition of MMRM analysis.

Means, mean changes, standard deviations, and ranges will be presented separately for Stage 1 and then for each Stage 2 treatment group over time. These endpoints will be evaluated within the three study treatment groups for the change from Stage 1 and Stage 2 baselines using a paired t-test and between study treatment groups using an unpaired t-test at each time; these p-values will be presented as descriptive statistics.

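### Section 13.10.5 has the study physician judge the primary relapse event while 5.1 and 8.2.5.1.1 give it to the adjudication committee, and nothing says whose decision or which date is analysed

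*Combined protocol and SAP*

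**What the plan says.** Section 13.10.4 makes the proportional hazards model in the ITT population the primary analysis. Section 13.10.5 starts the clock on the day of the ketamine infusion and says of the event: "Relapse will be judged in real-time by the study physician using baseline measures of depression and suicidality as a guide". The RAC does not appear there.

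Elsewhere the decision belongs to the RAC. Section 5.1 states "All relapses will be documented by the site physician and reviewed on a monthly basis by a Relapse Adjudication Committee" and "The Relapse Adjudication Committee (RAC) will determine whether the relapse met the primary endpoint criteria". Section 8.2.5.1.1 says "All site-defined relapses will be adjudicated by a Relapse Adjudication Committee (RAC) which will review documentation provided by the site for each incidence", and adds "The RAC is authorized to determine that relapse occurred even if the site does not make this determination". The text after Table 5 in 8.2.8 says "All site-reported relapse events will be reviewed by the RAC, and a determination made as to whether the event met study criteria for relapse", and section 11 says "The RAC will adjudicate each site reported instance of relapse for compliance the protocol definition of time to relapse".

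Section 8.2.5.1.1 lists three criteria: C-SSRS of 4 or more, MADRS subset of the BISS of 20 or more, or the treating physician's decision that the treatment plan must change. Section 13.5.1 also uses a new treatment plan and fixed scores. Section 5.1 instead words the score components as a return to baseline levels. On conduct, section 8.1 says "Subjects who meet study criteria for relapse at any point during the study will be withdrawn from the study".

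**The concern.** The primary event has two candidate owners and two candidate yardsticks. A programmer working from 13.10.5 would use the physician's call, made with baseline scores as guidance. One working from 8.2.5.1.1 would use the RAC's ruling against fixed thresholds. If the two always agreed, this would be a documentation gap. If they can disagree, event status and event time in the primary model depend on which section is followed, and that choice could still be open after the data are seen.

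A second issue is completeness. Adjudication protects a time-to-event endpoint only if qualifying cases reach the committee. Relapses that never reach it would count as event-free time.

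**Working it through.** **1. Who decides, and on what.**

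| Section | Decision by | Yardstick |
|---|---|---|
| 5.1 | RAC | new treatment plan, or return to baseline level |
| 8.2.5.1.1 | RAC | C-SSRS ≥4, MADRS subset ≥20, or physician-determined treatment change |
| 8.2.8, after Table 5 | RAC | study criteria for relapse |
| 11 | RAC | C-SSRS ≥4 and/or MADRS subset of 20; treatment change not listed |
| 13.5.1 | not stated | new treatment plan, C-SSRS ≥4 and/or MADRS subset of 20 |
| 13.10.5 | study physician | baseline measures as guidance |

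Section 9.4 adds real-time contact with the medical monitor to confirm a relapse. No row states which decision is the analysed event. No row gives the event date either: the qualifying rating, the treatment change, the site call and the monthly RAC ruling are all possible within a 42-day treatment period.

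**2. Can the yardsticks disagree?** Entry requires a MADRS subset of at least 20 (7.1). Response requires a reduction of at least 25% (6.2, 8.1.6). Taking integer scores, which is an assumption, and the smallest qualifying reduction:

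- Baseline 26: 0.25 × 26 = 6.5, so 7 points, giving 19. Below 20.
- Baseline 27: 0.25 × 27 = 6.75, so 7 points, giving 20. At the threshold.
- Baseline 28: 0.25 × 28 = 7 points, giving 21. Above the threshold, 7 points below baseline.

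So from a baseline of 27 upward, a minimal responder already meets the fixed MADRS criterion at randomization while well below baseline. More generally, for any baseline B above 20, a later score from 20 to B − 1 meets the fixed criterion without a return to baseline. The same applies to a subject enrolled at C-SSRS 5 who returns to 4. The documents do not give the distribution of baseline scores, so the number of such subjects is unknown.

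**3. What reaches the RAC.** Sections 5.1, 8.2.5.1.1, 8.2.8 and 11 describe relapses that the site documented, defined or reported. Section 12.1 adds reported emergence or worsening of suicidal ideation or behavior, also starting from a site report. No section gives the RAC the C-SSRS or BISS scores of a subject without a site report. A MADRS-subset crossing with no suicidal event and no site call therefore has no described route.

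**4. Illustration of size.** Inputs from 13.8.3: 56 K/N and 28 K/L evaluable, six-week relapse 30% and 70%, two-sided 0.05. Let m be the share of relapses permanently missed in both arms. This is an assumption; the documents give no value.

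Events E = (28 × 0.70 + 56 × 0.30)(1 − m). HR = ln(1 − 0.70(1 − m)) / ln(1 − 0.30(1 − m)). Power = Φ(√(E × 2/3 × 1/3) × ln HR − 1.96).

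| m | E | HR | Power, K/N vs K/L |
|---|---|---|---|
| 0 | 36.4 | 3.38 | 93% |
| 10% | 32.8 | 3.16 | 87% |
| 20% | 29.1 | 2.99 | 80% |

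Simulated three-arm Cox models (56/28/28, exponential times, 2,500 and 3,000 runs per scenario in two separate checks) gave 96% pairwise and 93% for both comparators with none missed; 92% and 85–86% at m = 10%; about 85% and 73–75% at m = 20%.

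Now suppose that a crossing persists and each visit independently misses it 20% of the time, with ratings on Days 7, 10, 14, 21, 28, 35 and 42. Only relapses late in the period have few chances of detection. In K/L, the share of relapses falling in Days 35–42 is (0.30^(35/42) − 0.30)/0.70 = 9.5%, and in Days 28–35 it is 11.6%. The share never caught is about 0.2 × 9.5% + 0.04 × 11.6%, or 2.4%, plus a small remainder. The same sum for K/N is about 3.5%. With roughly 3% missed, simulated power stays at 96% and 93%.

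**The case against.** The best defence is that the sections describe a sequence. A physician must act in real time because relapse leads to withdrawal and medical-monitor contact; the RAC then adjudicates monthly. Section 13.5.1, in the same statistics chapter, keeps the fixed scores, so 13.10.5 need not be a rival definition. This reading is reasonable, but the analysis section never states it or names the adjudicated event and date as those analysed. Nor does a sequence remove the difference in yardstick.

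Second, a reader might infer that the RAC sees only site-called relapses, so that adjudication can remove events but not add them. The documents do not support that. Section 8.2.5.1.1 expressly lets the RAC find a relapse that the site did not call, 12.1 sends it reported suicidal events as potential endpoints, and no section says that nothing else may be reviewed. Section 14.2 also has the medical monitor work with the RAC on safety signals. What remains is narrower: the authority to add events has no described case-finding process.

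Third, physician judgement is itself an endpoint criterion in 8.2.5.1.1. A site call that leads to alternative treatment will usually meet it, which limits the RAC's grounds for rejection. This stands, except that section 11 omits the treatment-change component.

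Fourth, an uncalled crossing would depart from the withdrawal rule in 8.1, and repeated ratings would catch most persisting crossings. This also stands, and it is why the power figures are illustrations only.

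**Conclusion.** The plan does not identify the event analysed in its primary test. Section 13.10.5 points to the physician guided by baseline, the other sections point to the RAC, and the fixed scores and the baseline guide can give the same subject different event status. That conclusion needs no assumed rate. It rests on the text and on the arithmetic for baselines above 20, reading baseline as the pre-infusion score.

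On case flow, the finding is limited to a missing process, chiefly for uncalled MADRS-only crossings. The documents do not show that relapses will be missed. The fall in joint power from about 93% to about 73–75% requires 20% of relapses to be missed permanently and equally in all arms; with later detection of persisting crossings it nearly vanishes.

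A reader might also infer that site calls rejected by the RAC are censored at withdrawal, which would be informative. No section sets that rule, and 8.1.7 and 9.5 ask for efforts to assess and follow subjects who leave early. The finding is that the handling of rejected calls is unstated.

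**What to change.** - Reconcile 13.10.5 with 5.1, 8.2.5.1.1 and 13.5.1. State that the RAC-adjudicated event is the analysed event, dated to the first qualifying rating or treatment change, and delete or reword the sentence on physician judgement. Settle whether the score components mean fixed values or a return to baseline, and say how a subject already at or above 20 at the 24-hour rating is treated.
- Derive the two score components from the eCRF at every visit and send each crossing to the RAC, blinded to arm, whether or not the site called relapse.
- State how a site call rejected by the RAC enters the primary analysis, given that the subject has already been withdrawn.
- Add a sensitivity analysis that counts site-called relapses as events on the site-call date.

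The cost is wording in the protocol, SAP and RAC charter, one database listing, and some extra cases at the monthly RAC meetings. The scores are already collected, so no new assessments are needed. The changes should be made before unblinding.

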13.10.6 Secondary Efficacy Endpoints

All of the instruments used to measure ASIB or depression constitute serial continuous and ordinal outcomes which will be analyzed using MMRM, which accounts for missing data and early discontinuations. These instruments are listed in Section 11.

The models will include treatment group, study visit, the interaction between study visit and treatment group, the baseline of the variable being analyzed, C-SSRS 24 hours post infusion (1, 2), age (<25 yrs, 25-39 yrs, >40 yrs), and gender as fixed effects. The reason for missing data will be evaluated as a condition of MMRM analysis.

13.10.7 Other Endpoints

The following additional endpoints will be recorded and analyzed for both study phases:

- Dose per treatment group
- All-cause discontinuation (and reason for discontinuation)
- Suicide rates
- Incidence of hospitalization and ER visits for disease-related outcomes
- Proportion of subjects who are treated with new SSRIs or have increased SSRI dosages
- Proportion of subjects who discontinue SSRIs or have reduced SSRI dosages.

Dose per treatment group will be displayed graphically over time per study treatment group. The percents decreasing and increasing over time relative to starting dose will be displayed per study treatment group.

Time to all-cause discontinuation will be displayed using a Kaplan-Meier lifetable and compared between treatments using a Wilcoxon-Gehan test.

Suicide rates will be evaluated using a Fisher Exact test to compare K/R vs. K/L and K/P.

The incidence of hospitalization and ER visits will be evaluated using a Wilcoxon Rank Sum test to compare each study treatment group.

The proportions of subjects discontinuing SSRIs or reducing SSRI dosages will be displayed graphically over time per study treatment group. The percents discontinuing SSRIs and reducing SSRI dosages relative to starting dose will be displayed per study treatment group.

13.10.8 Safety Endpoints

Separate safety analyses will be performed for Stage 1, Stage 2, and combined across stages.

Adverse events will be classified by MedDRA. For each study treatment, safety data will be collected and analyzed while on Stage 1 or Stage 2 treatment or until treatment-emergent adverse events are resolved. The type, incidence, timing (onset, duration), relationship, and severity of AEs will be reported for treatment-emergent and SAEs. Reasons for withdrawal due to AEs will also be reported. Narratives will be written for every AE classified as serious or associated with attempted suicide or death.

Planned surveillance findings according to the designated safety monitor will also be analyzed. Adverse event timing will be displayed graphically. Overall incidence will be compared using a two-sided Fisher Exact test. The cumulative number of such episodes will be evaluated using a Poisson regression model to compare study treatment groups controlling for C-SSRS 24 hours post infusion (1, 2), age (<25, 25-39, >40), and gender.

Vital signs and ECGs (means and mean changes from Stage 1 and Stage 2 baselines) will also be evaluated within treatment groups using paired t-tests and between study treatment groups using unpaired t-tests. Percents with abnormal vital signs, heart rate, QRS duration, PR interval, RR interval, QT, and QTcF will be reported. McNemar paired comparison tests will be performed within study treatment groups for the abnormal discordant percents while two-sided Fisher Exact tests will be performed to compare incidences between treatment groups.

Blood draws for chemistries and hematologies will be evaluated within and between study treatment groups. Abnormality rates will be presented relative to established site-specific normal ranges and whether or not the abnormality is clinically significant. McNemar paired comparison tests will be performed within study treatment groups for the abnormal percents while two-sided Fisher Exact tests will be performed to compare incidences between treatment groups.

14. DIRECT ACCESS TO SOURCE DATA/DOCUMENTS

14.1 Study Monitoring

Potential study sites will be evaluated by the sponsor in conjunction with the CRO to determine suitability for the proposed study. Information reviewed will include, but is not limited to, facility details and site capabilities, past performance in similar studies, investigator, and staff experience, ongoing studies at the site, projected enrollment in this study, and FDA or other agency audit findings. Study sites may be asked to complete a study-specific Site Selection Questionnaire and other documents for consideration for participation and CRO clinical study monitors may make a Site Qualification Visit prior to completing the evaluation process.

Upon completion of this evaluation, the sponsor will invite the chosen sites for participation.

Prior to subject enrollment, a study initiation visit will be completed at each investigational site to ensure the following: IRB approval has been obtained and documented prior to subject screening, the investigators and study personnel are appropriately trained and clearly understand the study, the investigators and study personnel accept the obligations incurred in undertaking this clinical investigation.

Raters proposed by each site will be evaluated on the basis of experience and education for each instrument used in the study. Raters with the appropriate levels of experience and education will be trained by an independent third party in the use of each instrument, and approved to administer that instrument in the study. Sites will not be approved to begin enrollment activities until they have at least one rater approved for each clinician-administered instrument.

Qualified clinical monitors or qualified contract monitors will conduct investigational site monitoring visits to ensure that all investigators conduct the study in compliance with the protocol and applicable regulations. The site will receive notification prior to each monitoring visit during the course of the study. It is expected that the investigator and/or sub-investigator and other appropriately trained study staff are available on the day of the visit in case any questions might arise.

Periodic monitoring visits will be made in accordance with the approved monitoring plan at all active study sites throughout the clinical study to assure that the investigator obligations are fulfilled and all applicable regulations and guidelines are being followed. These visits will assure that the facilities are still acceptable, the protocol and investigational plan are being followed, the IRB has been notified of approved protocol changes as required, complete records are being maintained, appropriate and timely reports have been made to the sponsor, CRO, and the IRB, and the site Principal Investigator is executing all agreed activities.

The sponsor retains the right to remove either the site-investigator or the investigational site from the study for issues of non-compliance with the protocol or regulatory requirements.

On one or more occasions, the study site may be inspected or audited by the sponsor representative or a third party. The investigator will be informed in advance of this visit.

Upon completion of the clinical study (when all subjects at the site have completed follow up visits, all data has been entered in EDC and cleaned, all queries resolved, and final electronic signatures have been obtained), a study closeout visit will be performed. Any unused study materials and equipment will be collected and returned to sponsor. The monitor will ensure that the investigator's regulatory files are up to date and complete and that any outstanding issues from previous visits have been resolved. Other issues which will be reviewed at this visit include: discussing retention of study files, possibility of site audits, publication policy, and ensuring that the investigator will notify the IRB regarding study closeout.

